10.0 Study Monitoring and Reporting Procedures

10.1 Adverse Event Reporting

10.1.1 Definitions

Adverse Event (AE): Any untoward medical occurrence associated with the use of a drug in humans, whether or not considered drug related. Progression of disease is considered the natural development of cancer in this study; therefore it is not considered as an adverse event.

Suspected Adverse Reaction (SAR): Adverse event for which there is a reasonable possibility that the investigational drug caused the adverse event (i.e., attribution to study drug of possible, probable, or definite).

Serious Adverse Event (SAE): An adverse event or suspected adverse reaction is considered "serious" if in the view of either the Investigator or sponsor, it results in any of the following outcomes:

- 1) Death,
- 2) A life-threatening adverse event,
- 3) Inpatient hospitalization or prolongation or existing hospitalization,
- 4) A persistent or significant incapacity or substantial disruption of the ability to conduct normal life functions,
- 5) A congenital anomaly/birth defect.
- 6) Important medical events that may not result in death, be life-threatening, or require hospitalization may be considered serious when, based upon appropriate medical judgment, they may jeopardize the patient or subject and may require medical or surgical intervention to prevent one of the outcomes listed in this definition.

Unexpected Adverse Event: An adverse event is considered "unexpected" if it is not listed in the investigator brochure or is not listed at the specificity or severity that has been observed.

10.1.2 GOG Reporting Requirements:

All investigators and ultimately the protocol Principal Investigator (PI) have the primary responsibility for AE identification, documentation, grading, and assignment of attribution to the study drug. It is the responsibility of the investigator to supply the medical documentation needed to support expedited AE reports in a timely manner. Investigators **MUST** immediately report to the sponsor any serious adverse event, whether or not considered drug related, including those listed in the protocol or investigator brochure and must include an assessment of whether there is reasonable possibility that the drug caused the event (21 CFR 312.64(b)). Please refer to Section 10.15 for reporting procedures.

Information regarding AEs and SAEs will be collected from the time of informed consent until 30 days from the last dose administered.

When possible, adverse events should be described in terms of a change in the baseline status or with a diagnosis or summary term rather than as individual symptoms. The Investigator is responsible for reporting SAEs to the appropriate Institutional Review Board (IRB) or other committees in accordance with local institutional and IRB policies.

10.1.3 Criteria for Determining Adverse Event Severity:

The descriptions and grading scales found in the revised NCI Common Terminology Criteria for Adverse Events (CTCAE) version 5.0 will be utilized for AE reporting.

10.1.4 Criteria for Determining Adverse Event Causality:

The following attribution categories will be used in assessing the relationship between the AE and the study drug:

RELATIONSHIP	ATTRIBUTION	DESCRIPTION
Unrelated to investigational	Unrelated	The AE is clearly NOT related to the intervention
agent/intervention	Unlikely	The AE is doubtfully related to the intervention
Related to investigational	Possible	The AE may be related to the intervention
agent/intervention	Probable	The AE is likely related to the intervention
	Definite	The AE is clearly related to the intervention

10.1.5 SAE Reporting to GOG and Novartis:

The investigator must report to GOG any serious adverse event, whether or not considered drug-related, within 24 hours of any site personnel becoming aware of the event. Please see the Data Management Manual for instructions for submitting SAE reports to GOG in Medidata Rave.

The GOG Regulatory Compliance Department will forward all SAE reports to Novartis within 24 hours of first awareness.

10.2 GOG Data Management Forms

The Case Report Forms (CRFs) noted in the Data Management Form Manual must be submitted through the Medidata Rave Electronic Data Entry System (www.imedidata.com). All amendments to CRFs must also be submitted through Medidata Rave.

Please refer to the Data Management Form Manual.

10.3 Safety Monitoring for Safety Lead-In

The formal safety monitoring process for the safety lead-in for this protocol includes bi-weekly teleconferences which will be scheduled with participating sites to discuss the patients enrolled on the safety lead-in. The site investigator or MD delegate is required to participate on the calls. In addition, it is recommended that the responsible Clinical Research Coordinator participate as well.

During the teleconference, each patient's drug doses, treatment delays, abnormal blood counts, and AEs/SAEs as documented on the Case Report Forms (CRFs) in Medidata Rave. The CRF data should be updated prior to each call. Sites should be prepared to discuss the following topics for each enrolled patient:

- Drug dosing (including total number of cycles)
- Treatment delays
- Dose modifications
- Adverse Events, Serious Adverse Events, DLTs
- Abnormal laboratory values
- Response evaluations
- Number of potentially eligible patients awaiting study

Please refer to the Regulatory Manual for more information regarding the safety lead-in.

11.0 Statistical Considerations

The intent of this this study is to assess the anti-tumor activity of the combination of letrozole + ribociclib in women with recurrent low-grade serous carcinoma of the ovary, fallopian tube or peritoneum measured by objective tumor response. This is a single-arm, open-label phase II study with a safety lead-in using an optimal flexible 2-stage design (33).

The targeted accrual for the first stage of the study will be 23 eligible and evaluable patients but permitted to range from 19 to 26 for administrative reasons. The cumulative targeted accrual for the second stage will be 48 eligible and evaluable patients but permitted to range from 44 to 51 for administrative reasons.

11.1 Study endpoints

11.1.1 Primary endpoints

The frequency of objective tumor response as assessed by RECIST 1.1.

11.1.2 Secondary endpoints

The frequency of clinical benefit (CR, PR, or SD).

The frequency and severity of adverse events as assessed by CTCAE v5.0.

Progression-free survival

Overall survival

11.1.3 Exploratory endpoints

Measurements of expression of ER, PR, and ki-67 and objective tumor response and clinical benefit.

Measurements of genomic signatures and objective tumor response and clinical benefit.

11.2 Anticipated annual accrual is approximately 31-39 patients based on GOG-0239.

The accrual duration will take approximate 7-9 months for the first stage without suspension of safety lead-in and 8-10 months for the second stage, separately. Additionally, the evaluation of patients with complete/partial response takes at least 16 weeks, and it can take even longer to evaluate patients with stable disease to determine whether they respond or not. Therefore, the duration for completion of primary endpoint will be approximately 13-15 months from activation of the study for the first stage, and 14-16 months from activation of the second stage for the second stage if the study advances to the second stage.

11.3 Study plan

Safety lead-in

The purpose of the safety lead-in phase is not to identify the MTD of the combination regimen. Rather it is being conducted to assure the safety of this regimen in the population of interest through the determination of cycle 1 DLTs. Patients will be dichotomized as either experiencing at least one DLT in cycle 1 (including delays in cycle 2 administration) or experiencing no DLTs at all in cycle 1.

After six patients have received a full cycle of treatment and are observed for the whole first cycle, the safety of the regimen will be assessed based on the dose limiting toxicities (DLTs) listed in Section 4.6. At most ten patients will be accrued before this safety evaluation takes place, and if necessary, accrual will be suspended at 10 patients in order to do this evaluation.

The probability of DLT (θ) will be assessed using a Bayesian interpretation of θ , in which θ is considered to be a random variable with a probability distribution. We combine the data observed in our trial with a prior probability distribution for θ to obtain a posterior distribution for θ . The DLT data is binomially distributed (DLT yes/no). The conjugate prior for the binomial distribution is the beta distribution, so we assume the prior for θ , $f(\theta)$, to be Beta(α , β). We specify our prior to have α =2 and β =6 which reflects the belief that the θ for the regimen is most likely around 0.1 to 0.25. Our interested target for the probability of DLT is 0.25.

Let n be the number of DLT-evaluable patients (i.e., had a DLT or treated for a full cycle), and x be the number of patients experiencing DLTs. The posterior for θ at the end of the safety lead-in is thus Beta($\alpha + x$, $\beta + n - x$). Consideration will be given to stopping the study if $Pr(\theta > 0.25 | x, n) > 0.5$, which corresponds to stopping if the number of patients with DLTs is greater or equal to critical value, r, i.e., 2 or more out of 6 or 7 patients, or 3 or more out of 8-10 patients. Table 11.1 shows the posterior probabilities of θ exceeding the target of 0.25 at the end of safety lead-in and corresponding critical values. These critical values are guidelines, but clinical judgment will be exercised, taking into account the nature of the toxicities and the likelihood of the toxicity being related to treatment.

Table 11.1: Posterior Probabilities of θ [Pr(DLT)] Exceeding the Target of 0.25 and Corresponding Critical Values for Consideration of Stopping for Toxicity

X					Pr(θ > 0.25	x,n)				
n	0	1	2	3	4	5	6	7	8	9	10
6	0.13	0.33	0.58	0.79	0.92	0.98	0.99				
7	0.10	0.28	0.52	0.74	0.89	0.96	0.99	1.00			
8	0.08	0.24	0.46	0.69	0.85	0.94	0.98	1.00	1.00		
9	0.06	0.20	0.41	0.63	0.81	0.92	0.97	0.99	1.00	1.00	
10	0.05	0.16	0.35	0.57	0.77	0.89	0.96	0.99	1.00	1.00	1.00

Phase II

The intent of this study is to assess the anti-tumor activity of the combination of letrozole + ribociclib measured by objective tumor response. Tumor response is dichotomized as response (i.e., complete or partial response) vs. non-response (i.e., stable disease, progressive disease, or unknown) and is assumed to have a Bernoulli distribution with a probability equal to π . Given a sample size, the number of tumor responses is binomially distributed with a given sample size and probability equal to π . Statistically, the evaluation of the study regimen efficacy measured by tumor response will be formulated through hypothesis testing via tumor response.

If combination proposed here has a true response rate of 10% or less, it would be considered of little clinical significance. Alternatively, if the true response rate were at least 25%, further investigation would be clearly indicated. Therefore, the primary hypotheses for this study can be formulated as follow:

H0: π ≤ 0.10,

H1: π ≥ 0.25,

where π is the probability of true tumor response, H0 is the null hypothesis and H1 is the alternative hypothesis. An optimal flexible two-stage design will be implemented to evaluate the primary hypotheses with average type I and type II error rates at 0.1 level, respectively (33). This design has early stopping guidelines that intends to limit patient accrual to inactive treatments and it permits the actual number of patients entered in each stage to vary slightly in order to

accommodate the challenges of coordinating a multicenter clinical trial while maintaining the levels of average type I and type II errors.

We will target an accrual of 23 eligible and evaluable patients in the first stage of this study, but in practice permit accrual to range from 19 to 26 patients due to administrative coordination. If there are more than 2 out of 19-25, or 3 out of 26 patients responding (complete or partial response) and medical judgment indicates, accrual to the second stage of the trial will be initiated. Otherwise, the study will be stopped and the treatment regimen will be classified as clinically uninteresting. If the study advances to the second stage, then an overall study accrual of 48 eligible and evaluable patients will be targeted, but permitted to range from 44 to 51 patients for administrative reasons. If more than 6 out of 44-45 patients respond or 7 out of 46-51 patients respond then the regimen will be considered worthy for additional investigation.

Under the assumed accrual ranges of 19 to 26 (stage 1) and 44 to 51 (cumulatively after stage 2), if the true probability of response is 10% (H0), then this study has a 64% probability of early termination and a probability of 10% of incorrectly declaring the study regimen interesting; if the true probability of tumor response is 25%, then the study has a 90% chance of correctly classifying the study regimen as being interesting.

The following table summarizes the accrual and decision guideline.

Stage of	Targeted	Limits of Actual	Max Number of Responses to
Accrual	Cumulative Accrual	Accrual	Reject Study Regimen
1	23	19-26	2/(19-25), 3/26
2	48	44-51	6/(44-45), 7/(46-51)

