4.6 Safety Lead-in

A review of safety will occur after the first 6-10 patients are treated and complete one cycle (including starting cycle 2 within the DLT constraints below) or have a DLT prior to completing the first cycle. Within the safety lead-in, patients who do not have a DLT and who do not complete cycle 1 will be replaced.

A dose limiting toxicity (DLT) is defined as an AE or clinically significant abnormal laboratory value assessed as unrelated to disease, disease progression, inter-current illness, or concomitant medications that occurs within the first 28 days of treatment with ribociclib and meets any of the criteria included in the table below. NCI CTCAE version 5.0 should be used for all grading.

Criteria for Defining Dose-Limiting Toxicities

Toxicity	DLT Criteria
Hematology	CTCAE grade 4 neutropenia lasting more than 7 consecutive days
	CTCAE grade 4 thrombocytopenia
	CTCAE grade 3 thrombocytopenia with bleeding
	CTCAE grade 3 or 4 febrile neutropenia
ECG QT interval	QTc interval ≥501 ms on at least 2 separate ECGs
Cardiac	Cardiac toxicity ≥ CTCAE grade 3
	Clinical signs of cardiac disease, such as unstable angina or myocardial
	infarction, or Troponin ≥ CTCAE grade 3
Gastro-intestinal	≥ CTCAE grade 3 vomiting ≥48 hours despite optimal anti-emetic therapy
	≥ CTCAE grade 3 diarrhea ≥48 hours despite optimal anti-diarrhea treatment
Hepato-biliary	≥ CTCAE grade 2 total bilirubin for more than 7 consecutive days
	≥ CTCAE grade 3 total bilirubin
	≥ CTCAE grade 2 ALT with a ≥grade 2 bilirubin elevation of any duration
	in the absence of liver metastases
	≥ CTCAE grade 3 ALT for >4 consecutive days
	CTCAE grade 4 ALT or AST
	Grade 4 serum alkaline phosphatase >7 consecutive days
Renal	≥ CTCAE grade 3 serum creatinine

ILD/pneumonitis	≥ CTCAE grade 3	
Any drug-related death		
Non-hematologic events	≥ CTCAE grade 3, except for the exclusions noted below:	
Exceptions to DLT criteria	Grade 3 alopecia	
	<5 days of CTCAE grade 3 fatigue	
	Grade 3 fever or infection without neutropenia <5 days duration	
	Grade 3 laboratory abnormalities that are responsive to oral supplementation or deemed by the investigator to be clinically insignificant	

CTCAE version 5.0 should be used for grading.

Optimal therapy for vomiting and diarrhea should be based on institutional guidelines with consideration of the prohibited medications listed in these protocol guidelines.

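### The safety lead-in trigger in 11.3 leaves out patients who have a DLT before finishing cycle 1, so it disagrees with 4.6, the synopsis and 11.3's own n, and moves the review later as such DLTs become more frequent

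*Combined protocol and SAP*

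**What the plan says.** The combined protocol and SAP states the trigger for the lead-in review in three places.

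- **Section 4.6 (and the synopsis, in the same terms):** "A review of safety will occur after the first 6-10 patients are treated and complete one cycle", counting also those who "or have a DLT prior to completing the first cycle". A patient without a DLT who does not complete cycle 1 is replaced.
- **Section 11.3, trigger sentence:** "After six patients have received a full cycle of treatment and are observed for the whole first cycle". It has no alternative limb for a DLT.
- **Section 11.3, stopping rule:** "Let n be the number of DLT-evaluable patients (i.e., had a DLT or treated for a full cycle"). This matches 4.6, not the trigger sentence in the same section.

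The rule uses a Beta(2,6) prior for the DLT probability. Stopping is considered when the posterior probability of a rate above 0.25 exceeds 0.5. That gives a critical value of two DLTs at n=6 or 7 and three at n=8 to 10 (Table 11.1). The critical values are described as guidelines subject to clinical judgment.

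Two provisions bound the lead-in. The first is a cap in 11.3: "At most ten patients will be accrued before this safety evaluation takes place". Enrolment pauses at that number if the review has not yet been done. Section 10.3 adds bi-weekly calls at which DLTs are discussed.

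**The concern.** Staff cannot follow both triggers once a DLT cuts cycle 1 short. Suppose two of the first six patients have such DLTs. Under 4.6 the review may be held at 2 of 6, which meets the guideline. Under 11.3 only four patients have received a full cycle, so two more completers are needed. If neither has a DLT, the review is held at 2 of 8, which does not meet it.

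Under the 11.3 wording, the more frequent these DLTs are, the later the review. That is the wrong direction for a lead-in meant to assure safety before the rest of stage 1 enrols.

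**Working it through.** **Step 1. Reproduce Table 11.1.** The posterior is Beta(2+x, 6+n−x), and the table gives its upper tail at 0.25.

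| n | x=2 | x=3 | Critical value |
|---|---|---|---|
| 6 | 0.584 | 0.794 | 2 |
| 7 | 0.521 | 0.742 | 2 |
| 8 | 0.461 | 0.686 | 3 |
| 9 | 0.405 | 0.630 | 3 |
| 10 | 0.353 | 0.574 | 3 |

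All printed cells agree to two decimals except n=9, x=2 (0.40499 computed, 0.41 printed), which affects no boundary. All critical values agree. The table is sound; the issue is which n it is entered at.

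**Step 2. Set up the two triggers.** Let θ be the DLT rate and q the share of DLT patients who do not receive a full cycle. The documents do not give q, so it is varied. Each evaluable patient is one of:

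- DLT, no full cycle: probability θq; raises n and x, not the completer count.
- DLT, full cycle: probability θ(1−q); raises all three.
- No DLT, full cycle: probability 1−θ; raises n and the completer count.

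The 4.6 trigger, taken at its minimum, reviews at n=6. The literal 11.3 trigger reviews at six completers or at ten patients, whichever comes first. Patients are taken one at a time and every path is enumerated exactly.

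**Step 3. The two ends have closed forms.**

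- Review at n=6, θ=0.25: 1 − 0.75⁶ − 6(0.25)(0.75⁵) = 1 − 0.178 − 0.356 = 0.466. At q=0 the literal 11.3 trigger gives the same.
- Literal 11.3, q=1: n at review is 6+x up to the cap, so two DLTs always mean 2 of 8. The guideline is met only if a third DLT precedes the sixth completer, which is P(Bin(8,θ) ≥ 3) = 0.321 at θ=0.25 and 0.685 at θ=0.40.

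**Step 4. Results across q.** Chance of meeting the guideline:

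| θ | Review at n=6 | 11.3, q=0.5 | q=0.75 | q=1 |
|---|---|---|---|---|
| 0.25 | 46.6% | 45.2% | 40.1% | 32.1% |
| 0.40 | 76.7% | 76.5% | 73.5% | 68.5% |
| 0.50 | 89.1% | 89.4% | 88.0% | 85.5% |

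Other results at θ=0.40:

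| | Review at n=6 | 11.3, q=0.5 | q=0.75 | q=1 |
|---|---|---|---|---|
| Boundary met at n=6 or 7 | 76.7% | 38.1% | 15.2% | 0% |
| Mean n at review | 6 | 7.45 | 8.27 | 9.00 |
| Ten reached without six completers | 0% | 3.3% | 15.0% | 36.7% |

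**Step 5. Bound on the delay.** The cap allows at most 10 − 6 = 4 further patients. At the 31 to 39 patients a year in 11.2, that is 4 × 52/39 = 5.3 weeks to 4 × 52/31 = 6.7 weeks.

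**The case against.** The strongest reply is that this is a wording slip with a recoverable intent: 11.3 defines n correctly a few lines later, and Table 11.1 starts at n=6. Several larger claims that a reader might infer do not hold.

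- **That the two-DLT boundary cannot be reached under 11.3.** This needs q=1. Section 11.3 counts as a DLT case a patient "experiencing at least one DLT in cycle 1 (including delays in cycle 2 administration"), and such a patient may have finished cycle 1. The DLT window covers any event "that occurs within the first 28 days of treatment with ribociclib", which includes the seven days off ribociclib. On the other side, many DLT criteria in 4.6 coincide with events for which 4.7.1 directs interruption or discontinuation, so q need not be small.
- **That the gap is 47% against 32%.** Those are the q=1 figures, set against 4.6 at its minimum n. Section 4.6 allows six to ten patients. At θ=0.25 its own chance of meeting the guideline is 46.6%, 55.5%, 32.1%, 39.9% and 47.4% for n=6 to 10, so that contrast is n=6 against n=8, a variation the plan tabulates.
- **That the two wordings give opposite answers on the same data.** 2 of 8 includes two further patients without a DLT, and a lower posterior is then correct.
- **That the review might never happen.** The cap forces it at ten patients.
- **That a third DLT should prompt an immediate review.** Table 11.1 is above 0.5 for x=3 at every n from 6 to 10, but this would be an extra look that neither section is shown to need. The calls in 10.3 already bring DLTs to discussion.

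What stands of the objection is that the size is modest unless q is high. It does not remove the contradiction, and the calls do not say when the rule is applied.

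**Conclusion.** The contradiction is real and needs no assumption: the 11.3 trigger differs from 4.6, from the synopsis and from the n it feeds. Followed literally, it delays the review more as cycle-shortening DLTs become more common. It also restricts the two-DLT boundary without making it unreachable, except at q=1.

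The effect on the chance of meeting the guideline runs from almost nothing at q=0.5 to about 14 percentage points at θ=0.25 and q=1 (46.6 − 32.1 = 14.5). At θ=0.40 and q=1 it is about 8 points (76.7 − 68.5 = 8.2). The effect on timing is clearer: at θ=0.40, between 1.45 and 3.00 extra patients on average for q from 0.5 to 1, and never more than four.

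These figures rest on an assumed q, on one-at-a-time entry and evaluation, and on 4.6 applied at n=6. They ignore patients replaced without a DLT, who might use places under the cap. Both 6.1 and 10.3 point to a Regulatory Manual for more on the lead-in, which is not among the documents.

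**What to change.** Reconcile the trigger sentence in 11.3 with 4.6, the synopsis and 11.3's own n. For example, it could read: *after six patients are DLT-evaluable, meaning that each has had a DLT or has been treated and observed through a full cycle*. The prior, Table 11.1, the critical values and the ten-patient cap need no change.

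The cost is one sentence. The review may be called slightly earlier than under the present 11.3 wording, with fewer patients observed when it is held.

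### The safety lead-in sets no DLT trigger before six evaluable patients, and Sections 4.6 and 11.3 leave open the number at which two early DLTs are judged

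*Combined protocol and SAP*

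**What the plan says.** Section 11.3 plans one assessment, after six patients have received and been observed for a full cycle, and limits entry before it: "At most ten patients will be accrued before this safety evaluation takes place, and if necessary, accrual will be suspended at 10 patients". The model is beta-binomial: "We specify our prior to have α =2 and β =6", and "Our interested target for the probability of DLT is 0.25". "Consideration will be given to stopping the study if" the posterior probability of a DLT rate above 0.25 is greater than 0.5. Section 11.3 translates this into critical values of "2 or more out of 6 or 7 patients, or 3 or more out of 8-10 patients", describes them as guidelines, and leaves room for clinical judgment. Table 11.1 has rows for 6 to 10 patients only.

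Section 4.6 and the synopsis place the review differently: "A review of safety will occur after the first 6-10 patients are treated and complete one cycle", or have a DLT before completing it. Section 10.3 adds bi-weekly calls with sites whose agenda includes "Adverse Events, Serious Adverse Events, DLTs", but it ties no count, pause or decision to them.

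**The concern.** The lead-in is there to show that the regimen is safe in this population before accrual runs freely. If two of the first few patients have a DLT, a review at 6 or 7 patients must meet the boundary whatever the next patients show. Nothing in the protocol then pauses entry, which may continue to the total cap of ten. Patients would start treatment after the answer at n=6 or 7 is already settled.

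There is a second problem. Because two DLTs cross at 6 or 7 but not at 8 to 10, continued entry can carry the same two events from above the boundary to below it. The plan does not fix the n at which the review is made, and its two descriptions of the review imply different values.

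**Working it through.** **Inputs.** From Section 11.3: prior Beta(2, 6), target 0.25, threshold 0.5, cap of ten. From Section 11.2: accrual of 31-39 per year. From Section 4.6: the 28-day DLT window. True DLT rates of 10%, 25%, 40% and 50% are assumed in order to show a range.

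**1. Reproduce Table 11.1.** With x DLTs in n patients the posterior is Beta(2+x, 6+n−x). For x=2, n=6 this is Beta(4, 10), and Pr(θ>0.25) = 0.584. For x=2, n=8 it is Beta(4, 12), giving 0.461, in line with the table row "8 0.08 0.24 0.46 0.69". Every cell agrees to two decimals, apart from a rounding tie at 2 of 9 (0.405 against the printed 0.41). The critical values are therefore right for the rule as stated.

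**2. Apply the same posterior across n=1 to 10.**

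| n | one DLT | two DLTs | three DLTs |
|---|---|---|---|
| 1 | 0.68 | – | – |
| 2 | 0.60 | 0.83 | – |
| 3 | 0.53 | 0.78 | 0.92 |
| 4 | 0.46 | 0.71 | 0.89 |
| 5 | 0.39 | 0.65 | 0.84 |
| 6 | 0.33 | 0.58 | 0.79 |
| 7 | 0.28 | 0.52 | 0.74 |
| 8 | 0.24 | 0.46 | 0.69 |
| 9 | 0.20 | 0.41 | 0.63 |
| 10 | 0.16 | 0.35 | 0.57 |

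Two DLTs exceed 0.5 up to n=7 and not from n=8. Three exceed it at every permitted review size.

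**3. Chance that a third DLT follows.** Given two DLTs in the first k patients, a review at n=8 to 10 crosses with probability 1−(1−θ)^(n−k). At θ=0.25 and n=8 this is 1−0.75³ = 0.58 for k=5 and 1−0.75⁶ = 0.82 for k=2. At n=10 it is 0.76 to 0.90.

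**4. The two definitions of the review.** Take two patients who have a DLT and do not finish cycle 1.
- Section 4.6 counts them toward the six. With four completers, n=6, x=2, posterior 0.58: the boundary is crossed.
- Section 11.3, read literally, waits for six who received a full cycle, yet its n also includes patients who had a DLT. That gives 2+6 = 8, x=2, posterior 0.46: the boundary is not crossed.

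**5. How often two DLTs come early.** P(at least 2 of 5) = 1−(1−θ)⁵−5θ(1−θ)⁴:
- θ=0.10: 1−0.590−0.328 = 0.08
- θ=0.25: 1−0.237−0.396 = 0.37
- θ=0.40: 1−0.078−0.259 = 0.66
- θ=0.50: 1−0.031−0.156 = 0.81

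**6. Patients entered after the second DLT.** This was simulated with Poisson accrual at 31-39 per year, DLT times uniform over 28 days, and the Section 4.6 trigger. At a 40% DLT rate the second DLT precedes the review in about 75-78% of lead-ins. About 5.0-5.4 patients have entered by then, against about 7.8-8.2 at the review. That is about 2.9-3.0 more patients over about 28-35 days. At a 10% rate, about 12-13% of lead-ins have a second DLT before the review. By arithmetic alone, the most that can enter after a second DLT is 10−2 = 8.

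**7. The literal Section 11.3 trigger.** Assume that DLT patients do not complete the cycle. Among lead-ins with an early second DLT, the boundary is then crossed at review in about 25%, 61% and 84% at true rates of 10%, 25% and 40%.

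**The case against.** A single-look lead-in of at most ten patients, governed by judgment, is a legitimate design. Investigators must join the bi-weekly calls on which DLTs are discussed (Section 10.3), and serious adverse events are reported within 24 hours (Section 10.1.5). The critical values are guidelines, and crossing one prompts only consideration of stopping. Sections 6.1 and 10.3 refer to a Regulatory Manual for more on the lead-in. It is not among the documents, so it cannot be shown that accrual would in practice continue. The exposure figures are largest at a 40% DLT rate, whereas the prior places the rate mostly around 0.1 to 0.25, and Section 1.6 reports two DLTs among 47 enrolled breast cancer patients. All of this stands, and it limits the size of the point. It does not supply a rule: the calls carry DLT data with no action attached.

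A reader might infer more than the documents support:
- **That a second early DLT makes the boundary certain to be met.** This is true only for a review at 6 or 7. At 8 to 10 a third DLT is needed.
- **That ten patients can enter after the second DLT.** Ten is the total, so at most eight can.
- **That the result is the same under Section 4.6 and Section 11.3.** Steps 4 and 7 show that it is not. Under the literal Section 11.3 reading, later patients do decide the answer.
- **That Table 11.1 could be extended to n=2-5 with a critical value of 2 under the unchanged 0.5 rule.** One DLT already gives 0.60 at n=2 and 0.53 at n=3, so that rule gives a critical value of 1 there.

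**Conclusion.** The point holds, with medium confidence, as a recommended change and not a fatal flaw. The protocol has no numerical trigger before six evaluable patients, a stated accrual hold only at ten, and two descriptions of the review that can place the same two DLTs on opposite sides of the boundary. The posterior results follow exactly from the plan's own prior and threshold. The exposure estimate of about three further patients at a 40% DLT rate rests on the assumed accrual process, DLT timing and Section 4.6 trigger. If the true rate is near 10%, an early second DLT is uncommon.

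**What to change.** 1. Add one sentence to Section 11.3 and mirror it in Section 4.6: if a second DLT is reported before six patients are evaluable, accrual is suspended and the safety review is brought forward. Leave the outcome of that review to the existing guideline and clinical judgment.
2. Reconcile Sections 4.6 and 11.3 on whether a patient with an early DLT counts toward the six, and state the n at which the review is made when further patients have already been entered.
3. Justify the trigger as early review against the boundary at n=6 or 7. Do not present it as new rows of Table 11.1. The prior, target, threshold and existing critical values stay as they are.

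The cost is a sentence in two places and one clarification; the Section 10.3 calls already collect the DLT information. The downside is an occasional short hold that is later lifted, including in lead-ins that would not have crossed at 8 to 10 patients. At a 10% DLT rate, about 12-13% of lead-ins would be held early under the Section 4.6 definition.

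### The lead-in toxicity posterior counts mid-cycle patients only if they have had a DLT, so it is biased upward unless everyone accrued has finished cycle 1 before the review

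*Combined protocol and SAP*

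**What the plan says.** Section 11.3 starts the assessment "After six patients have received a full cycle of treatment and are observed for the whole first cycle". On accrual it says: "At most ten patients will be accrued before this safety evaluation takes place". The count for the posterior is defined thus: "Let n be the number of DLT-evaluable patients (i.e., had a DLT or treated for a full cycle". The prior is Beta(2, 6). Stopping is considered if the posterior probability that θ exceeds 0.25 is above 0.5, which the plan converts to 2 or more DLTs of 6-7 patients, or 3 or more of 8-10. The plan calls these values guidelines, subject to clinical judgment. Table 11.1 covers n from 6 to 10.

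Section 4.6 and the synopsis describe the timing differently: "A review of safety will occur after the first 6-10 patients are treated and complete one cycle", with the alternative "or have a DLT prior to completing the first cycle". Section 4.6 also says that "patients who do not have a DLT and who do not complete cycle 1 will be replaced". The DLT window is 28 days, and completing the cycle includes starting cycle 2 within the DLT constraints.

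Neither section fixes the data cut or says how a patient who is under observation, DLT-free and not yet through cycle 1 is to be counted.

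**The concern.** Patients 7 to 10 can be part-way through cycle 1 when the sixth finishes. Under the definition of n, such a patient counts at once if she has a DLT and does not count at all if she is DLT-free so far. Whether she is included depends on her outcome, and the beta-binomial update does not allow for that. Her DLT is used and her DLT-free time is discarded.

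The critical value also rises from 2 to 3 between n=7 and n=8. Leaving out DLT-free patients can therefore hold n in the range where two DLTs are enough. A tolerable regimen could be flagged because of the day on which the data were cut.

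**Working it through.** **Inputs from the plan.** Prior Beta(2, 6), target 0.25, cut-off 0.5, critical values, trigger at six and cap at ten (Section 11.3); 28-day window (Section 4.6); accrual of 31-39 per year (Section 11.2).

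**Assumptions, not in the plan.** Poisson entry, DLT times uniform over 28 days, no replacements.

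**Step 1: reproduce Table 11.1.** Pr(θ > 0.25 | x, n) is the upper tail of Beta(2+x, 6+n−x).
- 2/6: Beta(4, 10) gives 0.584 (table 0.58).
- 2/7: Beta(4, 11) gives 0.521 (0.52).
- 2/8: Beta(4, 12) gives 0.461 (0.46).
- 2/10: Beta(4, 14) gives 0.353 (0.35).
- 3/10: Beta(5, 13) gives 0.574 (0.57).

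All entries agree to within 0.005 and the critical values follow. The table is correct for fully observed patients.

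**Step 2: one lead-in, two readings.** Ten patients are accrued. Six have completed cycle 1, one of them with a DLT. Of the four mid-cycle, one has had an early DLT.
- Plan's n at the review: x = 1+1 = 2, n = 6+1 = 7, posterior 0.52. Guideline met.
- If the other three finish DLT-free: x = 2, n = 10, posterior 0.35. Not met.

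**Step 3: how many are pending.** Entries per 28 days are 31×28/365.25 = 2.4 to 39×28/365.25 = 3.0. In simulation, with the review at the sixth evaluable patient, the mean number mid-cycle is 2.0-2.6 for θ from 0.10 to 0.25.

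**Step 4: chance of meeting the guideline.** The plan's n is compared with the same enrolled patients all followed through cycle 1 (at least 30,000 simulated lead-ins per setting, Monte Carlo error about 0.003, accrual 31-39 per year).

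| When the review takes place | θ=0.10: plan's n vs full follow-up | θ=0.25: plan's n vs full follow-up |
|---|---|---|
| Sixth evaluable patient | 15-16% vs 8-9% | 55-57% vs 44% |
| Sixth enrolled patient's day 28 | 15-16% vs 8% | 55-58% vs 44% |
| Sixth DLT-free completer | about 5% vs 6% | 38-39% vs 42-44% |
| All accrued patients resolved | no difference | no difference |

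In the third row the mean posterior probability at θ=0.25 is still slightly high, about 0.48 against 0.45, although crossing is slightly less frequent.

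**Step 5: sensitivity.** For the first two rows:
- DLTs confined to days 14-28: 51-52% vs 43-45% at θ=0.25.
- Accrual at an illustrative 15 per year: about 13% vs 11% at θ=0.10.

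**The case against.** The plan can be read so that the problem does not arise. Section 4.6 may mean that every accrued patient has finished cycle 1 or had a DLT before the review. Section 11.3 also refers to the posterior as of the close of the lead-in, tabulates n up to 10, and suspends accrual at ten if needed. On that reading there is no bias. This stands as a possible intention, but Section 11.3 triggers on six patients, and Section 4.6 does not say what happens to those enrolled beyond the sixth. If this is what is meant, it needs to be written.

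A second defence takes Section 11.3 to require six DLT-free completers, in which case crossing is not inflated. That reading fits the stated guideline poorly. It forces n ≥ 6+x, so two DLTs imply n ≥ 8 and the critical value of 2 of 6-7 could never be used.

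The consequence is also limited. The guideline is non-binding, the bi-weekly calls in Section 10.3 put each lead-in patient's status before the investigators, and where crossing is inflated the error leans toward stopping. The slot reservations and waiting list in Section 6.1 could slow early entry and shrink the gap. All of this stands.

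A reader might infer more than the documents support:
- **The rule inflates false stopping whatever the trigger, nearly doubling it at θ=0.10.** This holds only for the first two rows of the table, at the planned accrual rate and with uniform DLT timing. The plan does not name the sixth evaluable patient as its trigger.
- **A patient DLT-free on day 27 is settled on day 28, so the verdict can flip overnight.** Sections 4.6 and 11.3 also count the start of cycle 2, so day 28 does not necessarily resolve her.
- **Table 11.1 is wrong.** It is not; the issue is which patients are entered into it.

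**Conclusion.** The concern holds in a conditional form. The definition of n makes inclusion of mid-cycle patients depend on their outcome, so the posterior is biased upward whenever the review precedes full follow-up of everyone accrued. If the review falls at the sixth evaluable patient or the sixth enrolled patient's day 28, the chance of meeting the guideline rises by about 6-8 percentage points at θ=0.10 and 11-14 points at θ=0.25. Those sizes rest on the planned accrual rate and the assumption of uniform DLT timing; they shrink with later DLTs or slower entry. The effect on crossing reverses slightly if six DLT-free completers are required, and the bias vanishes if all accrued patients are resolved first. Because the documents do not settle which applies, the rule should be made explicit before the lead-in review.

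**What to change.** Reconcile Sections 4.6 and 11.3 on the event that triggers the review. Then state in Section 11.3 that x and n for Table 11.1 are computed on a fixed cohort: all patients enrolled at the trigger, each followed to a DLT or to the end of cycle 1, including the cycle 2 start criterion. The replacement provision in Section 4.6 can stay as it is. Prior, target, cut-off and critical values do not change.

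Three or more DLTs meet the guideline at every n up to 10 (the lowest value is 3/10 = 0.57), so that case need not wait for the remaining patients.

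The cost is a sentence or two of text and no extra patients or procedures. In the borderline case of two DLTs, the final reading may come up to about one cycle later.

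If an interim figure is wanted, pending DLT-free patients can be weighted by the fraction of the window observed. In the simulations, with the review at the sixth evaluable patient, this gives crossing of 10-11% at θ=0.10 and 44-46% at θ=0.25, against 8-9% and 44% with full follow-up. It assumes a uniform DLT hazard and gives too much DLT-free credit if DLTs come late. It is therefore an optional approximation and does not replace full follow-up.
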